**Check all that apply. If none apply, leave blank:**

This is a multisite study involving Mayo Clinic and non-Mayo Clinic sites.  
When checked, describe the research procedures/activities being conducted **only** at Mayo Clinic:

Mayo Clinic staff will be engaged in research activity at a non-Mayo Clinic site. *When checked, provide the location and a detailed description of the Mayo Clinic research staff involvement.*

This study is to establish and/or maintain an ongoing database or registry for research purposes only.

The research involves contact or interaction with subjects, for example, surveys, questionnaires, observation, blood draw.

The study involves photographing, audiotaping or videotaping subjects (and guests).

---

### Blood Collection

---

If this study involves prospective blood collection by finger, heel, ear stick or venipuncture, complete the following:

**From healthy, non pregnant, adult subjects who weigh at least 110 pounds.** For a minimal risk application, the amount of blood drawn from these subjects may not exceed 550ml in an 8 week period and collection may not occur more frequently than 2 times per week.

Volume per blood draw: \_\_\_\_\_ ml

Frequency of blood draw (e.g. single draw, time(s) per week, per year, etc.) \_\_\_\_\_

**From other adults and children considering age, weight, and health of subject.** For a minimal risk application, the amount of blood drawn from these subjects may not exceed the lesser of 50 ml or 3 ml per kg in an 8 week period, and collection may not occur more frequently than 2 times per week.

Volume per blood draw: \_\_\_\_\_ ml

Frequency of blood draw (e.g. single draw, time(s) per week, per year, etc.) \_\_\_\_\_

### Review of Chart, Images, Specimens

Provide the date range for collection of data and/or specimens that will be included in your research dataset.  
*Example: 01/01/2000 to 12/31/2013 or all records through mm/dd/yyyy.*

For a retrospective chart review, enter the date range: All records through date of sample acquisition; to correlate any medication, disease, or breath modifying factors, consent will be obtained to retrospectively review the patient's medical chart for correlation purposes. No identifying information will be used in association with the breath print. The breath print cannot be used to identify an individual.

**Check all that apply:**

- This study involves only data and/or specimens that exist at the time this application is submitted to the IRB (IRB submission date). No data or specimens will be collected beyond this date.
- This study involves only data and/or specimens that will be collected after submission to the IRB.
- The study involves data and/or specimens that exist at the time of submission to the IRB **and** data and/or specimens that will be collected after submission to the IRB, for example a study that includes collection of existing data and prospective collection of specimens.
- Data and/or specimens used in this study are collected under another IRB protocol. *When checked, provide the IRB number(s) from which the research material will be obtained. When appropriate, check the box below to attest that subjects have provided consent for future use of their data and/or specimens, as described in this protocol.*

IRB Number/s - Data Only: \_\_\_\_\_

IRB Number/s - Specimens Only: \_\_\_\_\_

IRB Number/s - Data and Specimens: \_\_\_\_\_

Note: When subjects provided consent for use of their data and/or specimens, as described in this protocol.

- Other data sources will be utilized in this study, e.g. receiving data/specimens from an external party. When checked, provide all data sources:

## Data Confidentiality, HIPAA Subject Identifiers

Review the list of subject identifiers below and, if applicable, check the box next to each subject identifier being recorded at the time you are collecting/abstracting data/specimens for use in this study.

**Subject Identifiers:** Individually identifiable information, including demographic data, that identifies the individual or for which there is reasonable basis to believe it can be used to identify the individual. NOTE: Identifiers apply to subjects enrolled in your study and to the subject's relatives, household members, employers, etc.

**Internal** refers to subject identifiers that will be included in the dataset maintained by the study team.

**External** refers to subject identifiers that will be shared with persons outside of the immediate study team, for example, sent to an external collaborator or shared with a national registry.

SUBJECT IDENTIFIERS Check all that apply	INTERNAL IDENTIFIER	EXTERNAL IDENTIFIER
Name		
Social Security number		
Medical record/patient registration number, lab accession, specimen or radiologic image number	X	
Study number, subject ID, or any other unique identifying number, characteristic or code that can be used to link the identity of the subject to the data	X	
Dates: All elements of dates [month, day, and year] directly related to an individual. Their birth date, date of death, date of diagnosis, etc. Note: Recording a year only is not a unique identifier.	X	
Medical device identifiers and serial numbers		X
Biometric identifiers, including finger and voice prints, full face photographic images and any comparable images		
Web Universal Resource Locators (URLs), Internet Protocol (IP) address numbers, email address		
Street address, city, county, precinct, zip code, and their equivalent geocodes		
Phone or fax numbers		
Account, member, certificate or professional license numbers, health beneficiary numbers		
Vehicle identifiers and serial numbers, including license plate numbers		
If None of the above identifiers will be recorded or maintained in the dataset and/or sent outside of the study team, please check "None".	 None	 None

## Statistical Information

*Note: Power analyses and study endpoints are not needed for a pilot or feasibility studies.*

No statistical information. *If checked, please explain:*

### Statistical Considerations

**Power Statement:** This initial portion of the study is a pilot/feasibility study with 25 subjects. Based on the experience of the eNose company who will be providing analytical and statistical support in pattern recognition a minimum of 25 positive and 25 negative samples are needed to start to discern separation. In other models, 100 positive and 100 negative training set is needed to create a robust diagnostic model. Further subjects beyond that, such as in multiple sites further fine tune the diagnostic model through pattern recognition learning algorithms (artificial neural networks).

Sample size calculations using 80% power with a 5% level of significance, assuming a 50% fasting / non-fasting prevalence, with a test with a minimum sensitivity and specificity of 80% suggests that about 450 patients are required to achieve statistical power. We will obtain 200 fasting and 200 non-fasting individuals to achieve aim for an accuracy greater than 85%. An additional blinded test group of 50 fasting and 50 non-fasting subjects will be used for model validation. Statistical modeling for training and validation will be performed by the eNose Company using artificial neural networks for pattern recognition as they have been already providing this support through our research collaboration. We will perform descriptive statistics of patient demographics and characteristics

**Data Analysis Plan:** The eNose company has proprietary expertise in digital signal processing, artificial neural network pattern recognition techniques, the basis which is on published algorithms and established methodologies. The eNose company in collaboration with the investigators will receive encrypted, de-identified digital signatures for training and create a diagnostic model. If the pilot study proves fruitful, this protocol will be expanded into a full study by increasing the enrollment to a full study.

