Preliminary studies show that signal separation can be detected within as few as 50 signals of 25 positive and 25 negative for training. A maturation process of pattern recognition occurs with 200 signals, 100 positive and 100 negative respectively. This is an initial pilot which can be expanded to the scale of a full study pending promising results. As we will be collecting positive and negative signals from the same patients, we anticipate subject numbers half that of the required signal training numbers.

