#### **Subject Information** – charts, records, images, or specimens are considered ‘subjects’

*Target accrual is the proposed number of subjects to be included in your study at your site. “Subjects” may include Mayo Clinic charts, records, or specimens, and/or charts, records, or specimens received at Mayo Clinic from external sources for collaborating analysis by the investigator under this IRB application:*

Target accrual: 1000 patients

Subject population: Any outpatient adult individual undergoing elective upper endoscopy who consents to study participation

Inclusion Criteria:

1. English speaking
2. Adult (18+) patient undergoing scheduled elective outpatient upper endoscopy
3. Willing and able to consent to research protocol
4. Fasting as required per routine instruction for endoscopy or non- fasting adults accompanying the patient who are able to provide informed consent
5. Able to breath for approximately 5 minutes pre procedure into the Aeonose device with a nose-plug on

Exclusion Criteria:

1. Non-fasting per protocol, or known to have had food or drink outside of routine protocol
2. Non-English speaking
3. < 18 years of age
4. Unable or unwilling to consent to research protocol
5. Inability to tolerate Aeonose breathing (such as those with claustrophobia, anxiety, nasal trauma, etc.)
6. Use of antibiotics or systemic immunosuppressants within three months prior to the date of endoscopy (intranasal and inhaled steroids are allowed)
7. Any prior chemotherapy for esophageal cancer
8. History of squamous cell carcinoma
9. History of gastric or esophageal surgery
10. Per PI discretion, any current medical problem that could alter intended study data collection.

Yes  No Will a Certificate of Confidentiality (COC) be obtained from NIH? If yes,

Who is obtaining the COC: Mayo Clinic investigator, study sponsor, other:

Explain why a COC is needed:

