## Study Design

Methods: *Describe, in detail, the research activities that will be conducted under this protocol:*

Fasting individuals undergoing upper endoscopy in the gastroenterology unit or non-fasting adults accompanying the patients will be enrolled for participation in Aeonose pre-procedural breath testing. These include elective inpatient procedures which have high risk of gastric content retention, but also have increased health risks due to active comorbidities.

Individuals consenting to participation of this study will be asked to provide a breath analysis using the Aeonose per standard acquisition protocol which spans 5 minutes of which the individuals breaths normally through a sterile disposable mouthpiece with sterile disposable air filters for 5 minutes during signal acquisition while wearing a nose plug. This may be completed prior to their endoscopic procedure.

The signals generated from each subject consist of a de-identified electronic breath-print will be analyzed by the investigators and the aggregate results matched using pattern recognition techniques to localize into fasting and non-fasting states. For the pilot portion of this study, the primary outcome is to establish separation of these signals in the initial cohort.

**Resources:** *Describe the available resources to conduct the research (personnel, time, facilities, mentor commitment, etc.):*

The lab group and study team consists of a full time laboratory researcher, gastroenterology clinical investigator fellows, and clinical research coordinators to support the study. The lab is based in the Alfred Main laboratory space. The lab group has already received on-site training by the eNose Company in the operation of the Aeonose. One Aeonose unit is immediately available for dedicated use towards this project and a sufficient supply of disposables (filters and mouthpieces) is already in stock for this project. The eNose Company who is a collaborating partner has dedicated further resources (more Aeonose units and disposables) as needed.

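### The pilot's 25 subjects reach the plan's minimum of 25 positive and 25 negative samples only if each person is tested twice, but the described enrolment gives one test per person

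*Combined protocol and SAP*

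**What the plan says.** The Power Statement under Statistical Considerations fixes the pilot's size: "This initial portion of the study is a pilot/feasibility study with 25 subjects". It then gives the device company's working minimum: "a minimum of 25 positive and 25 negative samples are needed to start to discern separation".

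The preliminary-studies paragraph under Purpose links the two figures. It says that "we will be collecting positive and negative signals from the same patients", and concludes that "we anticipate subject numbers half that of the required signal training numbers".

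The sections that set out who is enrolled and what is done to them read differently:

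- Study Design (Methods): "Fasting individuals undergoing upper endoscopy in the gastroenterology unit or non-fasting adults accompanying the patients will be enrolled for participation". Each consenting person is asked for a single breath analysis lasting five minutes. No second test in the other state is described.
- Subject Information, inclusion criterion 4, admits fasting patients "or non- fasting adults accompanying the patient who are able to provide informed consent".
- Inclusion criterion 5 requires that the person be "Able to breath for approximately 5 minutes pre procedure into the Aeonose device".
- Exclusion criterion 1 removes anyone "Non-fasting per protocol, or known to have had food or drink outside of routine protocol".

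For the later phase, the Power Statement counts 200 fasting and 200 non-fasting individuals, and a blinded test group of 50 of each.

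**The concern.** The plan contains two incompatible descriptions of where the non-fasting signals come from. In one, a patient gives a signal in each state. In the other, patients give the fasting signals and their companions give the non-fasting ones. The pilot's size was set under the first description, while the eligibility criteria and methods follow the second.

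Two things are at stake. Staff cannot tell from the protocol whether to enrol 25 patients tested twice, 25 people in total, or 25 patient-companion pairs. In addition, Study Design makes separation of the signals the pilot's primary outcome, and the Data Analysis Plan makes expansion depend on a promising pilot. If the enrolment text is followed with 25 people, that decision rests on half the number of samples the plan itself names as the minimum.

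**Working it through.** **Inputs**

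- Pilot size: 25 subjects (Statistical Considerations, Power Statement).
- Minimum samples: 25 positive and 25 negative (same place; the Purpose section gives the same 50 signals).
- Signals per subject under the Purpose section: 2, one in each state.
- Signals per subject under Subject Information and Study Design: 1. This is inferred from the either/or enrolment and the single breath analysis.

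**Step 1: reproduce the plan's figure**

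Required signals = 25 + 25 = 50.

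Subjects = required signals / signals per subject.

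With 2 signals per subject: 50 / 2 = 25. This reproduces the stated pilot size exactly.

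**Step 2: apply the enrolment and methods text**

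With 1 signal per subject: 50 / 1 = 50 subjects needed, which does not match 25.

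**Step 3: what 25 subjects deliver**

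| Design | Signals from 25 subjects | Share of the minimum of 50 | Best split by state |
|---|---|---|---|
| Both signals from each patient (Purpose) | 25 × 2 = 50 | 50/50 = 100% | 25 + 25 |
| Patients or companions, one test each (Subject Information, Study Design) | 25 × 1 = 25 | 25/50 = 50% | 13 + 12 |

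In the second row neither state reaches 25. The 13 + 12 split is the most favourable one, since the plan gives no split for the pilot.

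**Step 4: check which design the rest of the plan follows**

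The main phase counts 200 fasting and 200 non-fasting individuals, or 400 people if each is counted once. That fits separate people in each state, as in Subject Information and Study Design, and does not apply the halving rule.

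**Step 5: exclusion criterion 1**

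Inclusion criterion 4 admits non-fasting companions. Exclusion criterion 1 carries no restriction to patients and removes people who are not fasting. Taken literally, the companions are both admitted and excluded. If the exclusion prevails, that source of non-fasting signals disappears, so the 25 signals across both states in step 3 is already the generous reading.

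**The case against.** The strongest reply is that the 25 is not an error. The Purpose section states its rule, and the rule gives 25 exactly. That stands. A reader might infer that the pilot size was miscalculated, or that the pilot will certainly yield only 25 signals. The documents support neither, because they do not say whether the same-patient rule or the enrolment text prevails.

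One test per person is also an inference. Study Design does not forbid a second test, and it says the test may, not must, take place before endoscopy. That is why the yield is given as about 25. It does not remove the mismatch, because no second test is described anywhere.

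A reader might also infer that an enrolled patient can never give a non-fasting signal. That is too strong. The Purpose section recognises that patients who follow the fasting instructions may still retain food, and Study Design includes inpatients at high risk of retention. The plan does not say how such signals would be labelled. They would not bring 25 people with one test each up to 50 signals.

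It is tempting to turn the shortfall into a loss of power. The plan gives no pilot test, null value or success threshold on which such a figure could rest, and its Statistical Information section notes that pilots need no power analysis. The point here asks for none. It compares the pilot with a minimum that the plan itself states.

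Finally, 25 may have been meant as 25 patient-companion pairs. That would meet the minimum, but it is 50 people and the text does not say so.

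**Conclusion.** The contradiction holds. The stated pilot size meets the stated minimum only under a same-patient design that the eligibility criteria and methods do not carry out. Under the design they do describe, 25 subjects supply about 25 signals against a minimum of 50, with at most 13 in one state and 12 in the other.

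The count assumes one breath test per enrolled person, and that 25 subjects means 25 people and not 25 pairs. The 25-versus-50 count is the only size the documents support.

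The consequence is limited. A thin pilot makes the decision to expand less reliable, but the later blinded group of 50 fasting and 50 non-fasting subjects still guards the final claim. The point should be settled before pilot enrolment, since it determines who is recruited and how often each person is tested.

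**What to change.** Bring Purpose, Subject Information, Study Design and Statistical Considerations to one design.

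- **(a) If the companion design is intended:** restate the pilot in the Power Statement as 50 subjects, 25 fasting and 25 non-fasting with one breath test each (or as 25 patient-companion pairs, if that is meant). Delete the same-patient and half-number sentence under Purpose.
- **(b) If the paired design is intended:** keep 25 subjects, describe the second breath test in Study Design, and align inclusion criteria 4 and 5, exclusion criterion 1 and the companion wording with it.

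In both cases, state whom exclusion criterion 1 applies to.

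**Cost.** If 25 pairs were always meant, the change is wording only. Otherwise (a) makes the pilot look later, because 25 more people must be tested first (50 − 25 = 25). It adds subjects overall only if pilot subjects do not count toward the 200 + 200, which the plan leaves open. Option (a) also leaves fasting state mixed with patient or companion status, so a separation of signals could reflect either. Option (b) avoids that but adds one test per patient.

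### The plan does not require fasting and non-fasting breaths to be collected concurrently or balanced on each sensor unit, so period or unit can align with class and inflate the measured accuracy

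*Combined protocol and SAP*

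**What the plan says.** The Power Statement under Statistical Considerations sets the full study by class totals: "We will obtain 200 fasting and 200 non-fasting individuals to achieve aim for an accuracy greater than 85" (percent). It adds a blinded test group of 50 fasting and 50 non-fasting subjects and does not say when, or on which unit, that group is tested.

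Study Design takes the fasting class from patients having upper endoscopy and the non-fasting class from adults accompanying them. On equipment, its Resources paragraph says "One Aeonose unit is immediately available for dedicated use towards this project", and that the manufacturer "has dedicated further resources (more Aeonose units and disposables) as needed". The number and timing of further units are not given.

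The identifier table under Data Confidentiality marks "Medical device identifiers and serial numbers" as external only, and dates as internal only.

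Three other places bear on the point:
- The background text under Purpose says that both kinds of signal will come from the same patients, so that subject numbers are half the signal numbers. This does not agree with Subject Information, Study Design or the Power Statement.
- Endpoints lists the study of influencing factors as a secondary aim, but gives no method and names neither date nor unit.
- No section describes drift control, calibration between units, or the use of date or unit in the model.

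**The concern.** A neural network trained on two labelled groups uses any difference between them. If breaths of one class are mostly taken in one period or on one unit, then any sensor ageing, season, room air or unit-to-unit difference that shows in the signal becomes a usable clue to class. Scheduled patients and willing, non-fasting companions are two recruitment streams, and nothing in the plan holds them to the same pace. Once one total is full, every later test comes from the other class, including any on a newly added unit.

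Blinding the test group hides the labels but does not break such an association. If the 50 + 50 come from the same accrual stream as the training set, they carry the same alignment and the measured accuracy is too high. If they are collected later under different conditions, accuracy may fall for reasons that have nothing to do with fasting. In both cases the primary endpoint, whether the device distinguishes the two states, is answered less cleanly than the accuracy figure suggests. Analysis cannot fully repair this: in a period that contains only one class, period and class cannot be separated.

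**Working it through.** **1. The plan's own sample size.** The Power Statement takes 80% power, two-class balance, a significance level of 5%, and a floor of 80% for both sensitivity and specificity. From these it "suggests that about 450 patients are required to achieve statistical power". It states no null value, precision or sidedness, so 450 cannot be confirmed from the stated inputs.
- A two-sided 95% interval of ±5.2 points around 80% needs 1.96² × 0.16 / 0.052², or 228 per class and 456 in all, which is close.
- ±5 points gives 246 per class and 492 in all.
- A two-sided one-sample test of 80% against 70% gives 153 per class and 306 in all.

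None of these calculations allows for period or unit, so the figure does not bear on the concern either way.

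**2. A rule that knows only unit or period.** Let a be the share of fasting tests, and b the share of non-fasting tests, taken on unit A (or in period A). The best rule using that fact alone has accuracy 0.5 + |a − b|/2.
- Balanced, a = b: 50%. The chance of at least 86 correct out of 100 blinded subjects is about 4 × 10⁻¹⁴.
- 70/30: 70%, chance 0.0002.
- 80/20: 80%, chance 0.08.
- 85/15: 85%, chance 0.46.
- 90/10: 90%, chance 0.93.

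The chances assume that the blinded group has the same imbalance. Haphazard allocation of units would not create it: in 2,000 simulated sets of 200 + 200 with unit random with respect to class, the highest accuracy was 59%.

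**3. Unequal accrual.** Assume both classes start together and one accrues r times as fast. When the fast class is complete, a fraction 1/r of the slow class has been tested, and the rest follow in a single-class period. Calling every late test the slow class gives

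accuracy = [1 + (1 − 1/r)]/2 = 1 − 1/(2r).

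The result does not depend on the size of the totals, provided they are equal. The first two result columns assume that the sensor reveals the period perfectly, so they are upper bounds. If it is recognised correctly with probability s, accuracy is 0.5 + (2s − 1)(1 − 1/r)/2.

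| Assumed r | Accuracy, s = 1 | Chance of ≥ 86/100, s = 1 | Accuracy, s = 0.9 | Accuracy, s = 0.8 |
|---|---|---|---|---|
| 1.5 | 67% | 0.00001 | 63% | 60% |
| 2 | 75% | 0.005 | 70% | 65% |
| 3 | 83% | 0.29 | 77% | 70% |

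Setting 1 − 1/(2r) = 0.85 gives r = 1/0.30, about 3.3.

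**4. Added to a real signal.** Take a test that is truly 80% accurate, the plan's minimum. With 250 per class in one stream, the late single-class group has 250(1 − 1/r) subjects. Assume that the model recognises this group perfectly and is 80% accurate elsewhere:
- r = 1.5: (0.8 × 416.7 + 83.3)/500 = 83.3%
- r = 2: (0.8 × 375 + 125)/500 = 85.0%
- r = 3: (0.8 × 333.3 + 166.7)/500 = 86.7%

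The inflation is 3 to 7 points, and less with weaker recognition.

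**The case against.** The strongest reply is that the harm needs three things together: unequal accrual, a period or unit signature that the network can read, and a test group that shares the imbalance. The documents establish none of them. Companions attend with patients, at the same visit and at first with only one unit, which favours concurrent testing. Further units are conditional; if one is enough, the unit part of the concern disappears. If both signals come from the same person, as the background text says, the classes accrue one to one and the unequal-totals mechanism largely goes away. The larger study itself depends on the pilot.

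All of this stands as a limit on the size of the concern, but it does not remove it. Companions' attendance makes concurrent testing possible without requiring it. The same-patient statement conflicts with three other sections and does not specify the same day or the same unit.

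A reader might infer that the two totals do fill independently while units are being added, so that the model could pass 85% with no fasting signal at all. The documents do not support that. They are silent on the order of accrual, they make further units conditional, and they do not say which class would be slower. On the figures above, passing by this route alone needs an imbalance of about 85/15, or an accrual ratio above about 3.3, with near-perfect recognition of period or unit.

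**Conclusion.** The concern holds in a conditional form. The plan permits period or unit to align with class, and its blinded test group is no protection if it comes from the same stream. With perfect recognition of period, a period-only rule would reach 67% to 83% for accrual ratios of 1.5 to 3, still short of the target. The more realistic harm is inflation of a genuine signal: on the same assumption, an 80% test could read as 83% to 87%, which straddles the 85% aim. The accrual ratio, the recognisability of period or unit, and a shared imbalance in the test group are all assumptions.

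This is a worthwhile improvement to the design, not a demonstrated failure. It is separate from the confounding of fasting state with being a patient or a companion, which balanced collection does not remove.

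**What to change.** 1. In Study Design and the Power Statement, require fasting and non-fasting tests as same-day pairs on the same unit where possible, for example a patient and the accompanying adult. Where pairing fails, cap the running difference between classes on each unit.
2. Fill the training and blinded totals with both classes over the same calendar period, and state how and when the blinded group is drawn.
3. Amend the identifier table so that test date and unit serial number are held together in one dataset, for example by the study team. As marked now, neither the internal nor the external list contains both.
4. Report accuracy within unit and period, together with a negative-control model that uses only unit and date. With balanced collection that model should score about 50%. Name who runs these checks.
5. Reconcile the same-patient statement in the background with Subject Information, Study Design and the Power Statement.

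The cost is protocol wording, an accrual log, slightly slower recruitment of the faster class and a small identifier change. No extra subjects or procedures are needed.
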